4. BACKGROUND AND RATIONALE

The mental health of young people has significantly deteriorated in recent years. For example, in Austria in 2022, 73% of girls and 45% of boys suffered from moderate depressive symptoms (Haider et al., 2023). Other psychological symptoms were also very common, such as anxiety symptoms (57% in girls and 35% in boys) or sleep problems (34% in girls, 21% in boys) (Haider et al., 2023).

Although the causes of this trend are undoubtedly multifactorial and vary individually, daily smartphone use appears to have a particularly large impact (Humer et al., 2022). This is relevant because many countries, including Austria, are experiencing a rapid increase in daily smartphone use: According to the HBSC study, the average time spent on smartphones in 2022 was 5 hours per day, almost double what it was in 2018 (HBSC Study, 2022, HBSC Study, 2018). Additionally, there is at least a correlational relationship between screen time and mental health: a study of over 7000 young people showed that the likelihood of depressive symptoms increased up to 7 times with increasing smartphone use duration (Humer et al., 2022). Anxiety symptoms, sleep disturbances, disordered eating behavior, or stress also increased with increasing screen time, while life satisfaction and well-being decreased (Humer et al., 2022, Pieh et al., 2021). This demonstrates a stair-step effect: with each additional hour of daily screen time, the frequency of mental symptoms increases and well-being decreases (Humer et al., 2022).

A significant portion of daily screen time is due to the use of social media. These platforms are now an integral part of our daily lives, and their usage is increasing exponentially (Huang et al., 2018; Y. Sun et al., 2021). With the emergence of social media, the first scientific investigations into why we use social media were published (including Nadkarni et al., 2012). Excessive use of social media is associated with a variety of negative effects, such as decreased work performance (Kuss et al., 2014, Xanidis and Brignell, 2016), less healthy social relationships (Fox and Moreland, 2015, Müller et al., 2016), sleep problems (Koc & Gulyagci, 2013, Wolniczak et al., 2013), or lower life satisfaction (Blachnio et al., 2016, Hawi and Samaha, 2016).

More and more studies are highlighting the high addictive potential of social media (Sun et al., 2021). This seems to be present with most social media platforms, with TikTok (and presumably other short video formats) appearing to have particularly high addictive potential (Marengo et al., 2022).

This is consistent with earlier findings that reported a significant increase in boredom or craving (a term from addiction medicine describing intense desire for the addictive substance during withdrawal) when completely abstaining from social media for a week (Stieger et al., 2018). This study also showed that after just one week, there was no lasting change in usage behavior. After the intervention, participants resumed using social media as frequently as before (Stieger et al., 2018).

The reasons and causes for the intensive use of social media are certainly not fully understood. Activation of the brain's reward system through likes and positive interactions or the fear of missing out ("Fear of Missing Out" or FOMO) may repeatedly lead us to reach for our smartphones. But self-presentation, recognition, or "social comparison" can also play a role.

While social media can have advantages for entertainment, distraction, or contact with others, excessive use can lead to a range of negative consequences. In response, the term "Digital Detox" has emerged to emphasize the need for a conscious reduction in digital use.

5. OBJECTIVES AND OUTCOME MEASURES

Objective, Research Question, Procedure, and Design

Clinical Trial Protocol Template version 14.0

CONFIDENTIAL

© Copyright: The University of Oxford and Oxford University Hospitals NHS Foundation Trust 2018

The aim of the planned study is to reduce the screen time of healthy students in Austria over a period of 3 weeks and to investigate its impact on mental health.

Mental health indicators were evaluated in both groups at baseline, post-intervention, and at follow-up (t2). Participants will be informed weekly via App.

1. Main outcomes

Well-being (WHO-5): The validated German version of the World Health Organization well-being questionnaire (WHO-5) will be used.

Depressive symptoms (PHQ-9):Depressive symptoms will be assessed using the Patient Health Questionnaire (PHQ-9) in the validated German version.

Stress (PSQ-20): Stress will be assessed using the German version of the 20-item short-form of the Perceived Stress Questionnaire.

Sleep quality (ISI): Sleep quality will be assessed with the Insomnia Severity Index (ISI).

2. Additional outcomes

Problematic smartphone use (Smartphone Addiction Scale (SAS-SV)), anxiety symptoms (GAD-7), disordered eating (SCOFF), and Body Appreciation (BAS-2) will further be assessed.

Physical activity will be measured using a fitness tracker, as well as heart rate variability (HRV) and resting heart rate.

Objectives	Outcome Measures	Timepoint(s) of evaluation of this outcome measure (if applicable)
Depressive Symptoms (PHQ-9) Well-Being (WHO-5) Stress (PSQ 20) Sleep quality (ISI)	 Patient Health Questionnaire (PHQ-9) World Health Organization well-being questionnaire (WHO-5) Perceived Stress Questionnaire (PSQ-20) Insomnia Severity Index (ISI) 	At Baseline, post- intervention and at Follow-up.
 Problematic Smartphone Use 	 Smartphone Addiction Scale SCOFF BAS-2 GAD-7 	At Baseline, post- intervention and at Follow-up.

Disordered Eating	
 Body Appreciation 	
 Anxiety 	

6. TRIAL DESIGN

This study is a randomized, controlled trial (RCT) with a follow-up. There is no blinding and a two parallel group design. In order to keep drop outs in the control group low, participants in the control group will be offered intervention after follow-up (cross over).

7. PARTICIPANT IDENTIFICATION

7.1. Trial Participants

Inclusion Criteria

- Participant is willing and able to give informed consent for participation in the trial.
- Male or Female, aged 18 years or above (up to 29 yo).
- Health volunteer trial: be in good health (no diagnosed mental disorder, no ongoing medication or psychotherapy).

7.2. Exclusion Criteria

The participant may not enter the trial if ANY of the following apply:

- Diagnosed mental disorder
- Ongoing psychotherapy.
- Psychotropic drugs.
- Screen time daily less than 3 hours.

8. TRIAL PROCEDURES

8.1. Recruitment

Via social media, newsletter and notices at university.

8.2. Screening and Eligibility Assessment

The screening and eligibility assessment included sociodemographic data (age, gender), physical activity per week, statement about mental health disorders or therapy, as well as mental health indicators.

8.3. Informed Consent

Written and verbal versions of the Participant Information and Informed Consent will be presented to the participants. Participants have to sign must personally sign and date the Informed Consent form before participation

Written Informed Consent will then be obtained by means of participant dated signature and dated signature of the person who presented and obtained the Informed Consent. The person who obtained the consent must be suitably qualified and experienced, and have been authorised to do so by the Chief/Principal Investigator. The original signed form will be retained at the trial site.

8.4. Randomisation

Randomization will be processes through the ESMira® App. This App allows automatically randomization to one or the other group. After signing an informed consent form, participants joined the study in the ESMira18 app via QR-code. Randomization of ESMira is impervious to external influences.

8.5. Blinding and code-breaking

No blinding

8.6. Baseline Assessments

Main Outcomes:

- Patient Health Questionnaire (PHQ-9)
- World Health Organization well-being questionnaire (WHO-5)
- Perceived Stress Questionnaire (PSQ-20)
- Insomnia Severity Index (ISI)

Additional outcomes:

- Smartphone Addiction Scale
- SCOFF
- BAS-2
- GAD-7
- Physical activity (Fitness tracker).

8.7. Early Discontinuation/Withdrawal of Participants

Withdraw is possible at any time and without giving a reason. In case of withdrawal prior randomization, data won't be replaced. In case of withdrawel after randomization, missing data will be estimated by maximum likelihood estimation.

8.8. Definition of End of Trial

The end of trial is the follow-up measurement.

9. TRIAL INTERVENTIONS

Screen time (less than 2 hours per day) as well as social media use (less than 1 hour per day) should be reduced for a period of 3 weeks and the effects should be compared to a controlled group. A sample of N > 96 should be recruited through newsletter, notices and advertising on social media. The inclusion criteria are more than 3 hours of screen time per day, and no psychiatric illness for which they are being treated. After informing and signed the consent form, the participants have to download an App (ESMira®), which processes the whole study. The first step is to fill out sociodemographic data, smartphone usage and mental health questionnaires. After controlling for inclusion and exclusion criteria, ESMira will randomize into intervention (A) and controlled group (B). The participants in the intervention group (A) should continue their social media use and smartphone screen time unchanged for the first 10 days (Baseline.) After that (t1), the participants should limit their use of social media, such as Instagram, TikTok, Snapchat, Facebook, or similar sites to one hour per day and the complete screen time under two hours per day. To comply with that, participants should use the limiter function of there smartphone or download an additional app. Screen time of the smartphone and the social media use will be tracked automatically or via uploading a screenshot. At the end of the intervention (t2), the mental health questionnaires will be collected again. Afterwards there are no further tasks for the participants in the intervention group (A), screen time and social media use is possible again without restrictions. Screen time and social media use will be tracked until 3 month follow up (t3). During the study period participants will be asked to additionally wear a fitness tracker to measure daily movement as well as sleep behavior. The controls group (B) will be asked to continue their social media use and screen time unchanged to follow-up, after that the will be asked to fill out the mental health questionnaires again. After follow up, control group (B) will be offered to participate at intervention to keep drop outs and missing values low.

10. SAFETY REPORTING

Participants will be informed that discomfort, burdensome, withdrawal symptoms, or unrest might be possible during 3-week intervention period. They will receive an emergency phone number for a psychological support if the symptoms were too stressful.

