11. STATISTIC ANALYSIS PLAN

We will use the statistic software IBM SPSS Statistics (IBM Corp., Armonk, NY, USA) to analyze the data. χ^2 -Test and independent samples tests will be used to examine differences at baseline (t0) regarding age, gender, smartphone screen time, physical activity per week, and mental health indicators between the control and the intervention group.

Clinical Trial Protocol Template version 14.0

CONFIDENTIAL

To examine the effect of reduced smartphone screen time on the mental health indicators, repeated measurements ANOVAs (rm-ANOVA) will be applied. The primary hypotheses focuses on the difference between t0 (baseline) and t1 (post-intervention) between control group and intervention group (between group effect). In a secondary analysis, the follow-up time point (t2) will also be included.

Group allocation (control vs. intervention) will be the between-group factor, time will be the within-group factor (t0, t1, t2). Furthermore, a sub-group analysis (rm-ANOVA) will be applied of those, who strictly adhered to the 2h smartphone screen time limit during all three weeks. In case of baseline group-differences in the mental health indicators, these variables will be added as a covariate in the rm-ANOVA. If the sphericity assumption will be violated, the Greenhouse-Geisser correction will be applied. In the post hoc tests, Bonferroni correction will be applied to adjust for multiple comparisons.

Missing values will be estimated with via maximum likelihood estimation.

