12. DATA MANAGEMENT

The whole data collection procedure will be carried out through the ESMira App. ESMira is a tool for running longitudinal studies (ESM, AA, EMA, ...) with completely anonymized communication with participants and data collection. The following validated and frequently used mental health questionnaire will be used: Wellbeing (WHO-5), Depressive Symptoms (PHQ-9), Anxiety (GAD-7), Stress (PSS-10), Sleep quality (ISI), Eating disorder (EAT-8; SCOFF), and body awareness (BAD-2). These questionnaires will be collected at baseline, after intervention and at follow up. During the study, a weekly measurement of well being (WHO-5), body awareness (BAD-2), and stress (PSS-10) will be performed. What is ESMira? It works without a steady internet connection. All functionality of studies are saved locally in the app and saved data are cached and will be uploaded as soon as there is an internet connection. Personal Feedback: Researcher can set up complex charts that will be automatically calculated out of participants' data. These statistics can be either personalised to the participants or calculated out of all participants' data. Completely anonymous: Each participant gets a random participant id under which all data is collected. ESMira does not collect any personal data at any time. Anonymous Chat: Participants can communicate with the researcher from within the app and stay completely anonymous while doing so. Additionally, researchers can send important messages to all participants of a study. Free and open source: ESMira is developed as a project at Karl Landsteiner University to be used for our own studies and published for the community to use completely free of charge. Find out more at: https://github.com/KL-Psychological-Methodology/ESMira

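### The plan names discomfort, burden, withdrawal symptoms and unrest as possible harms but provides no item, log or analysis for them in either group, so the trial cannot report how often they occur

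*Combined protocol and SAP*

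**What the plan says.** Section 10 (Safety Reporting) says participants will be told that "discomfort, burdensome, withdrawal symptoms, or unrest might be possible during 3-week intervention period". The only further provision is this: "They will receive an emergency phone number for a psychological support if the symptoms were too stressful". The section gives no definition of an adverse event, no question, no time point and no reporting format.

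The measurement plan is spread over several sections:

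- The Synopsis, Section 5 and Section 8.6 list the PHQ-9, WHO-5, PSQ-20 and ISI as main outcomes. Of the additional scales, Section 5 says that "anxiety symptoms (GAD-7), disordered eating (SCOFF), and Body Appreciation (BAS-2) will further be assessed", alongside the SAS-SV. Section 5 places all of these at baseline, post-intervention and follow-up.
- Section 12 (Data Management) adds that during the study "a weekly measurement of well being (WHO-5), body awareness (BAD-2), and stress (PSS-10) will be performed".
- The Lay Summary and Section 9 add sleep and movement from a fitness tracker. Section 5 adds heart rate variability and resting heart rate.

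On analysis, Section 11 states: "To examine the effect of reduced smartphone screen time on the mental health indicators, repeated measurements ANOVAs (rm-ANOVA) will be applied". On leaving the study, Section 8.7 states: "Withdraw is possible at any time and without giving a reason".

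**The concern.** The trial's title already describes the result as an improvement in mental health. A reader of the eventual report will want to know what the restriction cost the people who followed it, and the protocol gives reasons to ask. Section 10 lists the possible symptoms, and Section 4 cites earlier work that "reported a significant increase in boredom or craving" when social media was given up for a week. The Synopsis also admits people whose screening scores are moderately raised.

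If the symptoms are not asked about, the numbers cannot be recovered afterwards. Section 12 describes data held under a random participant identifier with no personal data, and the plan describes no step that ties a support call to an identifier or group. What is at stake is the balance of benefit and harm in the report and the interpretation of drop-out in the intervention group. The test of the primary hypothesis is not at stake.

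**Working it through.** **Step 1. Is there a harm figure to reproduce?** No. The documents state no harm rate, no expected frequency and no sample size for harms. The check is therefore a reading of each section for the parts that a harm rate needs.

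| Needed for a harm rate | What the plan provides |
|---|---|
| Named symptoms | Yes, Section 10 |
| An item or instrument for them | None in the Synopsis, Sections 5, 8.6 or 12 |
| A log of spontaneous reports | None described; Section 12 has an in-app chat, not set up as a harms record |
| A cut-off for worsening on an existing scale | None |
| A tabulation or comparison by group | None in Section 11 |
| A reason for leaving | Not required, Section 8.7 |

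The denominator is available (the randomised groups). The numerator is not.

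**Step 2. Can the existing scales stand in?** Only in part. Weekly WHO-5 and stress scores, together with the PHQ-9, GAD-7 and ISI at three time points, would show a shift in the group average. They do not ask about withdrawal symptoms as such. Section 11 specifies repeated-measures ANOVA, which compares means, and does not say how the weekly scores will be analysed. A mean can improve while a minority gets worse.

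**Step 3. What would the planned size deliver if the symptoms were asked about?** Inputs: 40 completers per group (Synopsis and Section 11.1); 50 recruited per group (Synopsis, 40/(1 − 0.20) = 50); at least 96 in total, or 48 per group (Section 11.1, which matches 40 × 1.20 = 48). Full response is assumed.

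Upper 95% limit with zero reports: two-sided exact 1 − 0.025^(1/n); one-sided 1 − 0.05^(1/n). Chance of at least one report when the true rate is 5% (assumed): 1 − 0.95^n.

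| n per group | Two-sided upper limit | One-sided upper limit | Chance of at least one report at 5% |
|---|---|---|---|
| 40 | 8.8% | 7.2% | 87% |
| 48 | 7.4% | 6.1% | 91% |
| 50 | 7.1% | 5.8% | 92% |

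Exact two-sided intervals for assumed counts among 40: 4/40 (10%) gives 2.8% to 23.7%; 10/40 (25%) gives 12.7% to 41.2%; 20/40 (50%) gives 33.8% to 66.2%.

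Power for a group difference with 40 per group, two-sided 5%, normal approximation with a pooled null variance, and an assumed 5% rate in controls:

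- 10% in the intervention group: about 13%.
- 25%: Φ[(0.20 − 1.96 × 0.0798)/0.0766] = Φ(0.57), about 71%.
- 50%: over 99%.

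Common symptoms could therefore be estimated usefully at the planned size. Differences in uncommon ones could not be tested, only bounded.

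**The case against.** The strongest reply is that this is a three-week behavioural reduction in healthy adults who are forewarned and given a number to call, and that the trial collects a good deal of distress data. Weekly stress and well-being scores fall inside the restriction period; anxiety, depression and insomnia scores are repeated up to follow-up; the tracker records sleep; and the in-app chat offers a route for spontaneous reports. All of this stands. It rules out any claim that the trial has no information on distress. It does not supply a rate of the named symptoms. A deterioration cut-off could be applied to the scales later, but it would be chosen after the data were seen and would still not measure withdrawal.

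Several stronger readings are tempting and are not supported:

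- A reader might set the 31 days between the baseline and post-intervention questionnaires (10 + 21) against the one-week study in Section 4. Ten of those days precede any restriction, weekly measures fall within the other 21, and the time-point labels differ between sections.
- A reader might infer an early, passing peak of symptoms that is missed. Section 4 gives no time course, and it concerns complete abstinence, whereas this trial limits use. The gain from the remedy lies in what is asked, not in when.
- A reader might conclude that support calls go unrecorded, or that volunteered reasons for leaving are discarded. The plan is silent on both. Section 8.7 says only that a reason is not needed.
- A reader might suppose that support calls lower the outcome scores, or that symptom-driven drop-out flatters the intervention by a stated amount. The documents give nothing from which either effect could be sized.

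**Conclusion.** The point holds in a limited form. The protocol names four possible harms of its intervention and provides no item, log or analysis for any of them in either group. The trial could detect average worsening on overlapping scales. It could not report how often the named harms occurred, and it has no planned means of telling people who leave because of symptoms from people who leave for other reasons.

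The gap matters for reporting benefit against harm and leaves the primary comparison as specified untouched. It should be closed before data collection, since analysis cannot supply what was not asked. With the symptoms recorded, zero reports among 40 to 50 per group would bound the rate below about 8.8% to 7.1% (two-sided 95%; 7.2% to 5.8% one-sided). Those limits assume that everyone answers and that symptoms are reported when present; with non-response they widen. The harm rates used for power are assumptions, as the documents give none. The consent pages were not available to check, so any harms wording there is outside this conclusion.

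**What to change.** 1. **Weekly rating.** Add a short rating of the symptoms already named in Section 10 to the weekly ESMira prompt. Use identical items in both groups, starting in the baseline phase. State in Section 12 that both groups receive the prompt. In Section 11, add a table by group of the frequency and worst rating of each symptom, with exact 95% intervals.
2. **Leaving.** In Section 8.7, distinguish participants who stop limiting their screen time from those who leave the study. Keep sending the post-intervention and follow-up questionnaires to the first group. Offer an optional reason, with symptoms as one choice; this keeps the right to leave without explanation.
3. **Support and treatment.** At post-intervention and follow-up, ask both groups whether they have used the support number or started psychotherapy or psychotropic drugs, and tabulate the answers by group.

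The cost is a few extra items in an app prompt that already exists, with no visits or staff. Asking about symptoms will prompt some reports. Giving both groups the same items and starting before the restriction lets the comparison allow for that. None of this alters the intervention or its clinical management.

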11. STATISTIC ANALYSIS PLAN

We will use the statistic software IBM SPSS Statistics (IBM Corp., Armonk, NY, USA) to analyze the data. χ^2 -Test and independent samples tests will be used to examine differences at baseline (t0) regarding age, gender, smartphone screen time, physical activity per week, and mental health indicators between the control and the intervention group.

Clinical Trial Protocol Template version 14.0

CONFIDENTIAL

To examine the effect of reduced smartphone screen time on the mental health indicators, repeated measurements ANOVAs (rm-ANOVA) will be applied. The primary hypotheses focuses on the difference between t0 (baseline) and t1 (post-intervention) between control group and intervention group (between group effect). In a secondary analysis, the follow-up time point (t2) will also be included.

Group allocation (control vs. intervention) will be the between-group factor, time will be the within-group factor (t0, t1, t2). Furthermore, a sub-group analysis (rm-ANOVA) will be applied of those, who strictly adhered to the 2h smartphone screen time limit during all three weeks. In case of baseline group-differences in the mental health indicators, these variables will be added as a covariate in the rm-ANOVA. If the sphericity assumption will be violated, the Greenhouse-Geisser correction will be applied. In the post hoc tests, Bonferroni correction will be applied to adjust for multiple comparisons.

Missing values will be estimated with via maximum likelihood estimation.

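### Baseline tests on gender and screen time have no stated consequence and neither variable enters any model; fixing both as pre-specified covariates is a small, inexpensive improvement

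*Combined protocol and SAP*

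**What the plan says.** Section 11 of the combined protocol and SAP uses chi-square and independent-samples tests "to examine differences at baseline (t0) regarding age, gender, smartphone screen time, physical activity per week, and mental health indicators" between the arms. One rule follows from these tests: "In case of baseline group-differences in the mental health indicators, these variables will be added as a covariate in the rm-ANOVA". Nothing is said about what happens if age, gender, screen time or physical activity differ.

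The model is a repeated-measures ANOVA with two factors: "Group allocation (control vs. intervention) will be the between-group factor, time will be the within-group factor (t0, t1, t2". The primary question is stated as "The primary hypotheses focuses on the difference between t0 (baseline) and t1 (post-intervention) between control group and intervention group (between group effect".

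Section 8.4 says of allocation that "This App allows automatically randomization to one or the other group"; it mentions no stratification factor. Section 8.5 states that there is no blinding.

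Section 4 presents both variables as related to the outcomes. By gender it reports that "73% of girls and 45% of boys suffered from moderate depressive symptoms", with anxiety symptoms at "57% in girls and 35% in boys" and sleep problems at "34% in girls, 21% in boys". It also describes symptoms becoming more frequent with each extra daily hour of screen time.

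On timing, Section 8.2 collects gender at screening. Section 9 has participants report smartphone usage before the app randomises them, and places the 10-day unchanged-use phase after allocation.

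**The concern.** Four of the five kinds of baseline variable are tested to no stated purpose. Either the result is ignored, or the decision to adjust is left until the data have been seen, which is undesirable in an open-label trial with self-reported outcomes.

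Two of those four, gender and screen time, are the ones that the protocol's own background links to the outcomes. With about 40 completers per arm and no described stratification, the arms can differ noticeably in their share of women. At stake is how far the estimate, given such an imbalance, is displaced by it, and whether precision is forgone from variables that are already collected.

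**Working it through.** **The plan's figures.** No stated figure is in dispute. The planned effect d = 0.45 and the 40 completers per group (Section 3) serve as yardsticks. A repeated-measures calculation with f = 0.45/2 = 0.225, two time points, alpha .05, power .80 and the stated icc of .05 read as the correlation between repeated measures gives 38 per group for group-by-time and 42 for the group main effect. Both are close to 40.

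**Step 1: size of the gender gap.** Assumption: the Section 4 shares for girls and boys apply to this sample and can be read on a normal scale. Gap = z(share in girls) - z(share in boys).
- Depressive symptoms: z(.73) - z(.45) = 0.613 + 0.126 = 0.74 SD
- Anxiety (a secondary outcome): z(.57) - z(.35) = 0.176 + 0.385 = 0.56 SD
- Sleep: z(.34) - z(.21) = -0.412 + 0.806 = 0.39 SD

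**Step 2: how often the arms are imbalanced.** With 40 per arm, independent sampling and an assumed 50/70/80% women:

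| Difference in share of women | 50% | 70% | 80% |
|---|---|---|---|
| 10 points or more | .43 | .39 | .33 |
| 15 points or more | .22 | .18 | .12 |

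If the total number of women is instead held fixed and 80 people are split exactly 40/40, the ranges are 40-50% and 16-26%.

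**Step 3: would the baseline test flag it?** A 15-point difference is 6 women in 40. Uncorrected chi-square gives p = .18 (23 v 17 women), .14 (31 v 25) and .09 (35 v 29). None is significant.

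**Step 4: what reaches the treatment contrast.** Let rho be the pre-post correlation.

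*(a) Unadjusted t0-to-t1 change, gender effect constant over time.* The gap is the same at both times and cancels, so the shift is 0. A simulation with 40 per arm, 60% v 80% women, a gap of 0.74 SD, rho .5 and no treatment effect gave 0.01 SD with or without gender in the model.

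*(b) Outcome's t0 score in the model.* Shift = imbalance x gap x (1 - rho). At 15 points:

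| rho | Depressive symptoms | Share of 0.45 | Sleep |
|---|---|---|---|
| .3 | 0.15 x 0.738 x 0.7 = 0.078 SD | 17% | 0.041 SD |
| .5 | 0.15 x 0.738 x 0.5 = 0.055 SD | 12% | 0.030 SD |
| .7 | 0.15 x 0.738 x 0.3 = 0.033 SD | 7% | 0.018 SD |

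The same simulation (20 points, rho .5) gave 0.07 SD without gender and 0.01 SD with it; the formula gives 0.20 x 0.738 x 0.5 = 0.074.

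*(c) Gender predicts change.* If the gap grows by 25/50/100% between t0 and t1, the simulated shift in the change contrast at 20 points is 0.03/0.08/0.14 SD, and about 0 once gender is fitted.

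*(d) Group main effect tested instead.* Shift = imbalance x gap = 0.20 x 0.738 = 0.15 SD at 20 points, a third of 0.45.

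**Step 5: precision.** With p the share of women, the fraction of the variance left after t0 that gender removes is p(1-p)gap²(1-rho)² / [(1-rho²) + p(1-p)gap²(1-rho)²]. For depressive symptoms at p = .5 and rho = .3, the gender term is .25 x 0.545 x 0.49 = 0.067, and 0.067/(0.91 + 0.067) = 6.8%. At p = .8 and rho = .8 it is 1.0%. The range is therefore about 1-7% for depressive symptoms and 0.3-2% for sleep.

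The documents give no figure from which to size screen time, or gender for WHO-5 or PSQ-20.

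**The case against.** A reader might infer that a gender imbalance would be detected and then left to distort the result. The documents support neither half of that.

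- **Detection.** At the imbalances that occur often, the baseline test would usually be non-significant (Step 3).
- **Distortion.** The default analysis compares change between arms, and Section 4 reports only a cross-sectional difference in level, in girls and boys. No section says that gender predicts change over three weeks. Chance imbalance also does not bias a randomised comparison on average; its contribution is already in the standard error. At rho .5 the shift of about 0.055 SD is roughly 0.3 of the adjusted contrast's standard error of about 0.19 SD.

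The shifts in Step 4(b) also need two events together under the SAP's own rule: the gender imbalance, and a significant t0 difference that brings the score into the model. Simulated with 70% women, a 15-point imbalance coincided with a significant t0 difference in that outcome in only about 1-2% of trials. The 12-22% frequency must not be read as the frequency of the shift.

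The gap estimates are borrowed as well. They come from girls and boys, whereas this trial enrols adults aged 18-29 screened to exclude diagnosed or treated mental disorder.

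All of this stands and limits the point to a refinement. It does not remove the gap in the plan: four kinds of baseline variable are tested with no stated consequence, and the wording of the primary hypothesis leaves open whether the group-by-time term or the group main effect is tested.

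**Conclusion.** The point holds as a modest one. Section 11 tests age, gender, screen time and physical activity without saying what follows, and no model or described stratification uses gender or screen time. The plan is not biased on average.

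Conditional on a chance imbalance, gender could displace the estimate by one of three routes only: gender predicts change; the t0 score is in the model (about 0.03-0.08 SD for depressive symptoms at 15 points and rho .7 to .3); or the primary test is taken to be the group main effect. Fitting gender beside t0 would remove a further 1-7% (depressive symptoms) or 0.3-2% (sleep) of the remaining variance.

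These sizes rest on the Section 4 shares carrying over on a normal scale, and on the assumed share of women and pre-post correlation. For screen time the argument is qualitative: Section 4 links it to symptoms and it is the quantity being reduced, so its starting value may plausibly predict change.

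This is an inexpensive refinement, not an error that invalidates the test.

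**What to change.** In Section 11, replace the test-then-adjust logic for these variables with one sentence: gender and the smartphone screen time recorded at entry, before randomisation, are fixed, pre-specified covariates in every outcome model, whatever the baseline comparisons show. Keep the baseline table as description only.

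The sentence must name the pre-randomisation value. Under Section 9 the 10-day baseline phase follows allocation and the trial is open-label, so use during those days could already respond to the assigned group, and adjusting for it could introduce bias.

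Each covariate should enter with its time interaction, since otherwise it adjusts only the average level and not the t0-to-t1 contrast.

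Cost: one sentence and two between-subject degrees of freedom per model (with 80 completers and two groups, 80 - 2 = 78 becomes 76). No new data are needed, because both variables are already collected before allocation.
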